#### 8.1.1 Definition of Adverse Events (AE)

*Required text:* An **adverse event** (AE) is any symptom, sign, illness or experience that develops or worsens in severity during the course of the study. Intercurrent illnesses or injuries should be regarded as adverse events. Abnormal results of diagnostic procedures are considered to be adverse events if the abnormality:

- results in study withdrawal.
- is associated with a serious adverse event.
- is associated with clinical signs or symptoms.
- leads to additional treatment or to further diagnostic tests.
- is considered by the investigator to be of clinical significance.

*Study specific text:* For the purpose of this study, the following events will not be reported as AEs:

- Mild unrelated event.
- Moderate unrelated event. This would typically include physical events such as headache, cold, etc. that were considered unrelated to study participation.
- Substance use events, including:
  - Worsening of substance use
  - Need for higher level of care
  - Signs and symptoms of substance use withdrawal
  - Drug or alcohol craving
  - Medical events that are directly related to substance use

#### 8.1.2 Definition of Serious Adverse Events (SAE)

##### Serious Adverse Event

*Required text:* Adverse events are classified as serious or non-serious. A **serious adverse event** is any AE that is:

- fatal
- life-threatening

CONFIDENTIAL

- requires or prolongs hospital stay
- results in persistent or significant disability or incapacity
- a congenital anomaly or birth defect
- an important medical event

Important medical events are those that may not be immediately life threatening, but are clearly of major clinical significance. They may jeopardize the subject, and may require intervention to prevent one of the other serious outcomes noted above. For example, drug overdose or abuse, a seizure that did not result in in-patient hospitalization, or intensive treatment of bronchospasm in an emergency department would typically be considered serious.

All adverse events that do not meet any of the criteria for serious should be regarded as **non-serious adverse events**.

*Study specific text:* Given the population being enrolled in the study, it is expected that most participants will continue to have substance use (drug and alcohol), several may have overdose, and many may have hospitalizations or other treatments related to their substance use. These outcomes are being included in the 6 month follow-up assessment for exploratory analyses. When we learn about these outcomes at the time of follow-up assessments they will not be considered AEs/SAEs, but rather will be analyzed as for other exploratory study outcomes. We do not expect to learn about these outcomes in the interim (during the study before the 6 month follow-up visit) because we are not actively tracking participants' clinical status or health care use.

### 8.1.3 Definition of Unanticipated Problems (UP)

#### Unanticipated Problems Involving Risk to Subjects or Others

Any incident, experience, or outcome that meets all of the following criteria:

- Unexpected in nature, severity, or frequency (i.e., not described in study-related documents such as the IRB-approved protocol or consent form, not expected events given the eligible study population, etc.).
- Related or possibly related to participation in the research (i.e., possibly related means there is a reasonable possibility that the incident experience, or outcome may have been caused by the unique procedures involved in the research).
- Suggests that the research places subjects or others at greater risk of harm (including physical, psychological, economic, or social harm).

## 8.2 Classification of an Adverse Event

### 8.2.1 Severity of Event

The following guidelines will be used to describe adverse event severity.

- **Mild** – Events require minimal or no treatment and do not interfere with the participant's daily activities.
- **Moderate** – Events result in a low level of inconvenience or concern with the therapeutic measures. Moderate events may cause some interference with functioning.
- **Severe** – Events interrupt a participant's usual daily activity and may require systemic drug therapy or other treatment. Severe events are usually potentially life-threatening or incapacitating.

### 8.2.2 Relationship to Study Intervention

All events considered to be AEs will have their relationship to the study intervention/study participation assessed by the study PI, with consultation from the IRB, study sponsor, and/or study DSMB as appropriate. Determinations will be made based on factors including considerations of causality based on temporal relationships and clinical judgment. The degree of certainty about causality will be graded using the categories below:

#### CONFIDENTIAL

- **Definitely Related** – There is clear evidence to suggest a causal relationship between study participation and the AE, which would not have occurred in absence of study participation.
- **Probably Related** – There is evidence to suggest a causal relationship, and the influence of other factors is unlikely.
- **Possibly Related** – There is some evidence to suggest a causal relationship (e.g., the event occurred within a reasonable time after administration of the trial intervention). However, other factors may have contributed to the event (e.g., the participant's clinical condition, other concomitant events). Although an AE may rate only as "possibly related" soon after discovery, it can be flagged as requiring more information and later be upgraded to "probably related" or "definitely related," as appropriate.
- **Unlikely to be Related** – A clinical event unlikely based on temporality or clinical judgment to be related to the study. A temporal relationship to intervention administration may make a causal relationship improbable and/or there are other probable causes of the event (e.g., the participant's clinical condition, other concomitant treatments).
- **Not Related** – The AE is completely independent of study intervention administration, and/or evidence exists that the event is definitely related to another etiology.

### 8.2.3 Expectedness

The study PI will be responsible for determining whether an AE is expected or unexpected. An AE will be considered unexpected if the nature, severity, or frequency of the event is not consistent with the risk information previously described for the study intervention.

### 8.3 Time Period and Frequency for Event Assessment and Follow-Up

The occurrence of an AE or SAE may come to the attention of study personnel during study visits during study procedures as specified including participant surveys. Participants may also provide unsolicited information on AEs or SAEs during study visits. Given the low-risk nature of this study, AEs will not be monitored after the final study visit (6 month follow-up visit).

### 8.4 Reporting Procedures – Notifying the IRB

The PI will report the following types of events to the IRB and DSMB:

- AE or SAE AND unanticipated AND possibly, probably, or definitely related to the study. Study-specific descriptions of what will and will not be considered AEs or SAEs are provided in Sections 8.1.1 and 8.1.2.
- Anticipated adverse events occurring with greater frequency than expected.
- Knowledge of any death of a study participant, even if determined unrelated to the study.
- Other unanticipated problems involving risks to study participants or others.

These events will be reported according to the NYU Langone Health IRB's reporting guidelines.

#### 8.4.1 Adverse Event Reporting

AEs (see section 8.1.1) that are unanticipated and possibly/probably/definitely related to the study, or are occurring with greater frequency than expected, will be reported to the IRB using the appropriate forms via Research Navigator within 72 business hours of becoming known to the PI. Additionally, such AEs will be recorded on a summary report provided yearly to the IRB at the time of study continuation. The PI will have primary responsibility for reporting AEs, with assistance from the study RC.

#### 8.4.2 Serious Adverse Event Reporting

SAEs (see section 8.1.2) that are unanticipated and possibly/probably/definitely related to the study, or are occurring with greater frequency than expected, or any deaths of study participants will be reported to the IRB as quickly as possible after becoming known to the PI, and within 72 business hours. Reporting will be completed using the appropriate forms via Research Navigator. When appropriate and possible the PI will also attempt to discuss by phone with IRB staff. Additionally, such SAEs will be recorded on a summary report provided yearly to the IRB at the time of study continuation. The PI will have primary responsibility for reporting AEs, with assistance from the study RC.

CONFIDENTIAL

### **8.4.3 Unanticipated Problem Reporting**

In addition to AE and SAE reporting as specified above, other unanticipated problems (UPs) involving risks to study participants or others will be reported to the IRB within 72 business hours. UP reports will include the following information:

- Protocol identifying information: protocol title and number, PI's name, and the IRB project number;
- A detailed description of the event, incident, experience, or outcome;
- An explanation of the basis for determining that the event, incident, experience, or outcome represents an UP;
- A description of any changes to the protocol or other corrective actions that have been taken or are proposed in response to the UP.

### **8.4.4 Reporting of Pregnancy**

Not applicable; we are not testing participants for pregnancy.

### **8.5 Reporting Procedures – Notifying the Study Sponsor**

Adverse Events (AEs) deemed to be possibly, probably, or definitely related to the study will be reported to the NIDA PO at least once per year. At a minimum, this report will describe the event, when it occurred, and the outcome/resolution. If there were no AEs, a statement that no AEs occurred will be included in the yearly progress report or communicated to the PO in writing. Serious Adverse Events (SAEs) are not expected but—if determined to be possibly, probably, or definitely related to the study—would be reported to the NIDA PO within 72 hours of the event by email. At a minimum, this notification would include a brief explanation of the SAE and when it occurred. A written follow up would be sent within 5 business days of the event, after consultation with the site IRB. The written follow up would include information on the date of the event, what occurred, actions taken by project staff, planned follow up, whether participant will continue in the study, and any recommendations from the IRB. In addition, any negative IRB actions relevant to the study will be reported to the NIDA PO within 72 hours of the IRB action.

### **8.6 Reporting Procedures – Participating Investigators**

Not applicable (this is a single-center trial).

### **8.7 Study Halting Rules**

Given the low-risk nature of our intervention and the fact that this is a pilot feasibility study we do not anticipate any circumstances under which the study would need to be halted.

### **8.8 Safety Oversight**

This is an extremely low-risk study. The study has a small DSMB consisting of independent investigators (not otherwise affiliated with the study) who have the appropriate expertise to advise on issues of study safety, ethics, and data management. The DSMB meets once yearly to review study data and draft a report, which is sent to the study sponsor. The study sponsor has previously approved the DSMB process for the parent grant for this study (K23 DA039179). Additionally, any concerns or recommendations for changing or halting the study made by the DSMB will be reported promptly to the IRB.

DSMB members include:

- [name], Associate Professor, Department of Emergency Medicine
- [name], Assistant Professor, Department of Population Health

It is the responsibility of the Principal Investigator to oversee the safety of the study. This safety monitoring will include careful assessment and appropriate reporting of adverse events as noted above.

## **9 Clinical Monitoring**

Given that this is an extremely low risk study that does not involve medical procedures or treatments, external clinical monitoring and/or independent audits are not appropriate. The study PI will be responsible

CONFIDENTIAL

This material is the property of the NYU School of Medicine and Langone Health Medical Center. Do not disclose or use except as authorized in writing by the study sponsor

for ensuring internal quality management of study conduct, data collection, documentation, and completion. This monitoring will occur on an ongoing basis in conjunction with other study staff to ensure timely recognition of any potential problems. The study RC will conduct weekly data quality assurance checks using procedures developed in conjunction with the PI, and results of these QA checks will be discussed weekly with the PI or immediately if any significant problems are identified.

## **10 Statistical Considerations**

### **10.1 Statistical and Analytical Plans**

There will not be a formal SAP for this small feasibility pilot study.

### **10.2 Statistical Hypotheses**

As the primary endpoints for this study are measures of feasibility that are descriptive in nature, there are no formal or testable null or alternative hypotheses. For exploratory endpoints of housing and substance use outcomes, we will test the hypothesis that participants will have improved in these outcome measures at the time of the 6-month follow-up survey compared to the baseline survey. However, as noted previously, the study is not being powered to formally test these hypotheses and, therefore, any such analyses will be considered purely exploratory in nature.

### **10.3 Analysis Datasets**

A single analysis dataset will include all participants. The analysis dataset will consist of the following:

- Baseline and follow-up participant surveys and other study instruments.
- Participant locator form information.
- Information collected from follow-up/tracking phone calls and/or NYULH SendSafe emails with participants and/or applicable service providers, as previously described.
- Participant information extracted from approved external sources (with participant consent) including the Bellevue Hospital Center EMR and the NYC DHS CARES dataset.

### **10.4 Description of Statistical Methods**

#### **10.4.1 General Approach**

This is a single-arm pilot study to examine feasibility. Methods appropriate for a feasibility study, including descriptive statistics, and simple bivariate and multivariable analyses will be used.

#### **10.4.2 Analysis of the Primary Efficacy Endpoint(s)**

There are not primary efficacy endpoints for this study. Rather, the primary endpoints are measures of intervention/study feasibility. The main analyses for feasibility will involve simple descriptive analyses examining endpoints including:

- Number of patients approached, number (percent) screening positive for unhealthy alcohol or drug use, number (percent) screening positive for homelessness risk.
- Number (percent) of those approached who are eligible for the study. Number (percent) reasons for ineligibility.
- Number (percent) of those eligible who agree to participate. Number (percent) reasons for refusal.
- Basic characteristics (e.g., gender, age, race, primary drug vs. alcohol use) of those who were eligible vs. ineligible and agreed and did not agree to participate using descriptive statistics and bivariate analysis.
- Number and location of referrals made for homelessness prevention and/or substance use services. Number and types of homelessness prevention and other services actually received. Length of time between the ED intervention and receipt of services.
- Participant satisfaction and self-efficacy measures as assessed at baseline and 6 month follow-up visits.

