ED patients with unhealthy alcohol or drug use may be at even higher risk of homelessness than other ED patients given the strong associations between homelessness and substance use. One study of 19,055 ED patients found that those who screened positive for substance use had very high rates of homelessness or unstable housing: 22.8% were currently living in a shelter or on the streets and an additional 36.1% were “doubled up” with family or friends. With more than 5.1 million visits for substance use-related problems annually and nearly one-third of ED patients screening positive for unhealthy alcohol or drug use, EDs may be important sites for interventions to prevent homelessness among substance users. Given that only a small subset of substance users and people who are homeless access specialty substance treatment programs, and that both populations face barriers to accessing primary care, ED-based prevention programs have the potential to reach more people—and potentially more vulnerable people—than interventions at other sites.

Summary. EDs have potential as important health care delivery settings for homelessness prevention efforts among all patients, and particularly among patients with unhealthy alcohol or drug use. In earlier research, we developed an empirically-based homelessness risk screening tool (HRST) to identify ED patients at high risk for future shelter entry. We also conducted qualitative interviews with ED patients to learn about their pathways to homelessness and thoughts about future homelessness prevention

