#### **4.2 Study Endpoints**

##### **4.2.1 Primary Study Endpoints**

Given the primary study objective around feasibility and acceptability, the primary study endpoints represent a constellation of feasibility and acceptability measures that will be informative in modifying/developing a future larger intervention study. We will track the number of patients approached, the number screening positive for unhealthy alcohol or drug use, the number screening positive for homelessness risk, and the number of those eligible for the intervention who agree to participate. We will track reasons for study ineligibility and refusal, and will compare basic characteristics (e.g., gender, age, race, drug and alcohol use) of those who agreed and did not agree to participate. We will also track the number and location of referrals made for homelessness prevention and/or substance use services, the number of appointments kept, the number and types of homelessness prevention and other services actually received, and the length of time between the ED intervention and receipt of services. We will track the ability to contact patients for the 6-month follow-up interview (e.g., number of calls needed). Data sources for these feasibility endpoints include the *ED-Home Baseline Screening and Survey* (see attachment) and the participant tracking and follow-up information that will be documented on REDCap (*ED-Home Follow-up Procedures Form* and *ED-Home Tracking Form*) and using a tracking log in Excel that will be used internally to manage participant status, attempts of contact with participants, attempts of contact with providers, and necessary follow-up steps; no protected health information will be recorded on the Excel tracking log. In addition, we will gather information on acceptability of and satisfaction with both the overall intervention and its individual components from patients both immediately after the intervention is provided (while they are in the ED) and at the 6-month follow-up interview using a series of intervention assessment questions contained in the

CONFIDENTIAL

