Upon approaching patients, RAs will explain that they are conducting a research study and obtain patient verbal assent to complete screening questions for study eligibility. A standard screening tool will be used, with RAs guided through the screening and entering question responses in real-time using REDCap (see ED-Home Baseline Screening and Survey attachment). Patients who are found eligible for the study will be invited to participate. The informed consent process will be conducted by the study RC and will include explaining to patients what will occur in the study, what information they will be asked to give, and who receives and can use this information (see ED-Home Informed Consent and ED-Home Key Information Sheet attachment). Written informed consent is required for study participation. Participants will sign two consent forms; one copy to retain themselves and the other for study records. For participants in whom capacity to complete informed consent is questionable, a validated consent capacity quiz will be completed (see ED-Home UBACC attachment) and/or research staff will discuss with the patient’s treating provider prior to obtaining written informed consent.

Participant retention will be enhanced in the following ways:

- Detailed locator information will be collected from each participant. This information will include multiple contact phone numbers and other information that will enhance our ability to contact participants for follow-up procedures. See ED-Home Locator Form attachment for full details.
- Participants will be given a study contact card and sticker to allow them to contact study staff proactively as needed, for example, if their contact information has changed. See ED-Home Study Contact Card and Sticker attachment.
- Follow-up participant contact including follow-up visit reminders will occur in the manner and schedule outlined in the ED-Home Baseline Procedures flow chart in the Schematic of Study Design section.

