### **7.3.1 Screening**

Screening for study eligibility will occur during a patient's Bellevue Hospital ED visit. The process for screening is provided in the *ED-Home Pilot Baseline Procedures* flow chart in the Study Schema section of this protocol. The process for screening is fully described in protocol Section 5.4 and the attachment *ED-Home Baseline Screening and Survey*.

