## **12 Quality Assurance and Quality Control**

Multiple steps will be taken toward quality assurance (QA) and quality control (QC).

- All study staff, including RAs and RC, will be thoroughly trained both in overall GCP and human subjects protections and in study-specific procedures.
  - Formal training will occur prior to the study beginning recruitment.
  - Continuous training will occur in weekly staff team meetings.
- RAs will be closely supervised by the RC, with PI oversight. The RC will be supervised by the PI.
- A SOP document will clearly outline all study procedures, including QA/QC procedures.
- Multiple QA/QC protections are built into REDCap data collection software being used for this study, including forced question entry (i.e., specified questions cannot be left blank), automatic logging of all activities in REDCap including any entry changes, and study staff permission rules.

CONFIDENTIAL

- All paper forms, including consent forms, will be regularly reviewed (both at the time of initial completion and at least weekly) for completeness.
- Weekly QA/QC reviews between the PI/RC will include:
  - Review of numbers of patients approached, eligible/ineligible, refused, participated.
  - Review to ensure that all eligibility classifications were made correctly.
  - Review for missing or out of range data.
  - Review of any potential QA/QC issues identified by any study staff member (which did not warrant more immediate discussion).

The PI and RC will oversee QA and QC efforts.

The investigational site will provide direct access to all trial related sites, source data/documents, and reports for the purpose of monitoring and auditing by the sponsor, and inspection by local and regulatory authorities.

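### Does Section 10.4.2 need a second denominator to separate low eligibility from refusal of screening?

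*Combined protocol and SAP*

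**What the plan says.** Section 10.4.2 (headed as the primary efficacy analysis, though it covers feasibility) sets out the recruitment funnel in three steps. It starts with the number approached and the "number (percent) screening positive for unhealthy alcohol or drug use", with a matching item for homelessness risk; neither percentage has a stated denominator. Next comes "Number (percent) of those approached who are eligible for the study", followed by reasons for ineligibility. Then comes "Number (percent) of those eligible who agree to participate", followed by reasons for refusal. A further item compares eligible with ineligible patients, and those who agreed with those who did not, on basic characteristics. The whole list is introduced as a set of included examples, not as a closed set.

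Section 5.4 says that on approaching a patient the research assistant will "obtain patient verbal assent to complete screening questions for study eligibility". Written consent comes later, for those found eligible.

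Section 4.2.1 adds: "We will track reasons for study ineligibility and refusal". The weekly quality review in Section 12 has this item: "Review of numbers of patients approached, eligible/ineligible, refused, participated". Section 7.3.1 states: "The process for screening is fully described in protocol Section 5.4 and the attachment" holding the screening form; it also points to the baseline flow chart. Neither the form nor the flow chart could be read in the text available for this review.

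**The concern.** There are two points at which a patient can say no: before the screening questions, and at consent. The two percentages with stated denominators cover approach-to-eligible and eligible-to-agreed. Refusal at the first point falls inside the first percentage, where it looks the same as failing the criteria. No visible section names a count of patients who declined or completed screening, and none says at which stage a refusal is counted.

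This could matter because Section 3 intends the pilot to shape a larger multisite study. If few patients qualify, the remedy lies in criteria or sites. If many decline sensitive questions about substance use and housing in a busy department, it lies in how they are approached. A low eligible-per-approached figure, taken alone, does not say which. Section 10.1 plans no separate SAP, so Section 10.4.2 is the main statement of how these primary endpoints are summarised.

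**Working it through.** **The plan's only related figure.** Section 10.5 equates about 40 enrolled over 6 months with 1–2 per week. 40 / 26 weeks = 1.54 per week, which agrees. No number is stated for patients approached, screened or declining.

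**What the reported percentage contains.** Let A be approached, D declined before assessment, E eligible and I assessed and found ineligible. Then

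E/A = [(A − D)/A] × [E/(A − D)].

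The first factor is willingness to be screened and the second is eligibility. E/A alone does not identify either.

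**Whether the listed counts identify them.** If ineligible means assessed and failed, then D = A − E − I, and A, E and I all follow from items in Section 10.4.2 or the weekly review in Section 12. Illustration, all inputs assumed except the 40 enrolled: consent of 80% among those eligible gives 40 / 0.80 = 50 eligible, with 1,000 approached.

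| Declining | Assessed (A − D) | I | A − E − I | E/A | E/(A − D) |
|---|---|---|---|---|---|
| 0% | 1,000 | 950 | 0 | 5.0% | 5.0% |
| 10% | 900 | 850 | 100 | 5.0% | 5.6% |
| 20% | 800 | 750 | 200 | 5.0% | 6.3% |
| 40% | 600 | 550 | 400 | 5.0% | 8.3% |

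E/A is the same in every row, which is the concern. The residual A − E − I differs in every row and equals the number declining, which is the answer to it. If decliners were instead coded as ineligible, the residual would be 0 throughout, and separation would rest on a decline entry among the reasons for ineligibility.

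**Size against sampling error.** The Wilson 95% interval for 50/1,000 is 3.8% to 6.5% (upper limit 6.53%). E/(A − D) reaches 6.53% when D/A = 1 − 5.0/6.53 = 0.23. This is only a yardstick, since the interval belongs to E/A and not to E/(A − D).

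**Screen-positive percentages.** Section 2.1 cites "nearly one-third of ED patients screening positive for unhealthy alcohol or drug use". If one-third of those screened are positive and the percentage is taken over approached, it reads 33.3%, 30.0%, 26.7% and 20.0% at 0%, 10%, 20% and 40% declining. The unstated denominator therefore needs a label in the report. The counts needed to compute it either way are the same as above.

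**Whether the obvious replacement is better.** Dividing by patients who completed screening would drop those ruled out before finishing it under Section 5.2, such as patients who do not speak English or are in custody. They are ineligible, not decliners, and removing them would inflate percent eligible. The denominator that isolates refusal is A − D, which keeps them in.

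**The case for a change.** The strongest reply is that subtraction depends on a definition the protocol does not give. Criterion 5 in Section 5.1 makes willingness to consent part of eligibility, so a patient who declines screening could formally be logged as ineligible. The residual would then be zero at any decline rate. Refusal in the Section 12 review carries no stage, and in Section 10.4.2 reasons for refusal follow the agreement item, so they read as refusal of participation. An open list permits more reporting but does not promise it. Section 17 places the screening form outside the protocol, so what it captures does not fix a denominator.

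Part of this stands: the visible text does not define ineligible or refused by stage, and a reader given only percent eligible could not apportion it. But the plan does not report that figure alone. Comparing eligible with ineligible patients on drug versus alcohol use presupposes that the ineligible were assessed. Section 4.2.1 tracks refusal without limiting it to consent, and reasons for ineligibility are tabulated, so a decline logged there could appear as its own reason. The baseline flow chart belongs to the protocol itself and may show a decline branch; what could not be read cannot be counted as absent.

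**Conclusion.** No change to the plan is called for. The factual premises are right: assent precedes screening, percent eligible is taken over patients approached, and the visible text names no count of screening declines. It does not follow that the two causes cannot be told apart. The planned counts separate them if ineligible means assessed and failed, or if declines are logged as a reason.

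Following Section 10.4.2 as written produces no wrong result. Eligible per approached says what it is, no decision rule uses it, and enrolled per approached, consent among those eligible and satisfaction are all unaffected. The size of any ambiguity is unknown and is zero if nobody declines. In the assumed example it stays within the sampling interval until about 23% decline.

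This is a detail that analysts fill when they draw the participant flow: they give the number who declined before eligibility was known, and show percent eligible over approached minus those decliners beside the per-approached yield. The conclusion rests on the stage of refusal being recoverable from REDCap, the screening form or the flow chart, which could not be confirmed from the text available.
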